### **8.3.7.11 Serious and Opportunistic Infections**

Completion of the infection page in the eCRF is required for each infection reported as an AE or SAE (including the common cold). The sponsor will identify infections considered to be opportunistic ([Appendix 15.3](#)).

## **8.4 Pregnancy**

Refer to [Appendix 15.1](#) for contraceptive guidance. Pregnancy testing should be performed as described in the SoA ([Table 1-1](#)) for pregnancy testing at the study site. WOCPB and all female adolescents will be instructed to take a urine pregnancy test before dosing with IP while away from the study site and to report any positive pregnancy test result while away from their study site to their study site.

### **Male Participants with Partners Who Become Pregnant**

- The investigator will attempt to collect pregnancy information on any male participant's female partner who becomes pregnant while the male participant is in this study. This applies only to male participants who receive IP.
- After obtaining the necessary signed ICF from the pregnant female partner directly, the investigator will record pregnancy information on the appropriate form and submit it to the sponsor within 24 hours of learning of the partner's pregnancy. The

female partner will also be followed to determine the outcome of the pregnancy. Information on the status of the mother and child will be forwarded to the sponsor. Generally, the follow-up will be no longer than 6 to 8 weeks following the estimated delivery date. Any termination of the pregnancy will be reported regardless of fetal status (presence or absence of anomalies) or indication for the procedure.

### **Female Participants Who Become Pregnant**

- The investigator will collect pregnancy information on any female participant who becomes pregnant while participating in this study. The initial information will be recorded on the appropriate form and submitted to the sponsor within 24 hours of learning of a participant's pregnancy.
- The participant will be followed to determine the outcome of the pregnancy. The investigator will collect follow-up information on the participant and the neonate, and the information will be forwarded to the sponsor. Generally, follow-up will not be required for longer than 6 to 8 weeks beyond the estimated delivery date. Any termination of pregnancy will be reported, regardless of fetal status (presence or absence of anomalies) or indication for the procedure.
- While pregnancy itself is not considered to be an AE or SAE, any pregnancy complication or elective termination of a pregnancy for medical reasons will be reported as an AE or SAE.
- A spontaneous abortion (occurring at <22 weeks gestational age) or still birth (occurring at >22 weeks gestational age) is always considered to be an SAE and will be reported as such.
- Any poststudy pregnancy-related SAE considered reasonably related to the IP by the investigator will be reported to the sponsor as described in [Section 8.3.1.3](#). While the investigator is not obligated to actively seek this information in former participants, he or she may learn of an SAE through spontaneous reporting.
- Any female participant who becomes pregnant while participating in the study will discontinue the study treatment.

## 8.5 Pharmacokinetics

Blood samples will be collected for analysis of lebrikizumab PK at time points indicated in the SoA ([Table 1-1](#)). Samples will be collected before dosing on a dosing day, and serum concentration of lebrikizumab will be measured.

Procedures for PK sample collection, processing, handling, and shipping will be described in the laboratory manual. Samples will be analyzed at a laboratory approved by the sponsor. Concentrations of lebrikizumab will be assayed using a validated enzyme-linked immunosorbent assay.

Bioanalytical samples collected to measure lebrikizumab concentrations will be retained for a maximum of one year following the last participant visit for the study. During this time, samples remaining after the bioanalysis may be used for exploratory analyses such as bioanalytical assay validation or cross-validation exercises.

Lebrikizumab concentration data that may unblind IP of any participant will not be reported to study sites or to personnel who are blinded to study data unless that participant's treatment arm assignment has been unblinded to facilitate their care. For details of PK sample retention, see [Section 12.8.1](#).

## 8.6 Pharmacodynamics and Biomarkers

### 8.6.1 Exploratory Blood and Nasal Biomarkers

Blood and nasal samples will be collected for exploratory biomarker research (eg, CC motif chemokine ligand 17/thymus and activation regulated chemokine, or other cytokines/chemokines).

Biomarker samples will be collected according to the SoA ([Table 1-1](#)) and as detailed in laboratory manual provided separately to sites. Samples will be analyzed at a laboratory approved by the sponsor.

These samples may be used for one or more of the following study areas: research on the drug target, variable response to lebrikizumab, mechanisms of action of lebrikizumab, research methods of lebrikizumab or CRSwNP, validating diagnostic tools or assay(s) related to lebrikizumab or CRSwNP, or pathways associated with CRSwNP. For details of sample retention, see [Section 12.8.1](#).

Sample retention enables use of new technologies, response to regulatory questions, and investigation of variable response that may not be observed until later in the development of lebrikizumab or after lebrikizumab becomes commercially available.

### **8.6.2 Total Immunoglobulin E**

Blood samples will be collected to discern total IgE levels to explore responder variability within the study and to track response variability to lebrikizumab. Samples will be collected according to the SoA ([Table 1-1](#)) and as detailed in the laboratory manual provided separately to study sites. For details on sample retention, see [Section 12.8.1](#).

## **8.7 Immunogenicity Assessments**

Blood samples will be collected for analyses of ADA to determine antibody production against lebrikizumab at the time points indicated in the SoA ([Table 1-1](#)) and following procedures detailed in the laboratory manual for sample collection, processing, handling, and shipping. For details of immunogenicity sample retention, see [Section 12.8.1](#).

The actual date and time (24-hour clock time) of each sample collection will be recorded. To aid interpretation of results, a blood sample for PK analysis will be collected at the same time points. All samples for immunogenicity should be taken predose when applicable and possible.

Immunogenicity will be assessed by a validated assay designed to detect ADA in the presence of lebrikizumab at a laboratory approved by the sponsor. Antibodies may be further characterized by their ability to neutralize the activity of lebrikizumab. Treatment-emergent ADA (TE ADA) are defined in [Section 9.5.8](#).

Immunogenicity data that may unblind any participant to the IP will not be reported to study sites or to personnel who are blinded to study data unless that participant's treatment arm assignment has been unblinded to facilitate their care.

## **8.8 Medical Resource Utilization and Health Economics**

Medical research utilization and health economics parameters are not evaluated in this study.

## **8.9 Genetics**

A whole blood sample will be collected for pharmacogenetic analysis where local regulations allow, according to the SoA ([Table 1-1](#)) and following procedures detailed in the laboratory manual for sample collection, processing, handling, and shipping. For details of sample retention, see [Section 12.8.1](#).

### **Use/Analysis of DNA**

- Genetic variation may impact a participant's response to IP, susceptibility to, and severity and progression of disease. Variable response to IP may be due to genetic determinants that impact drug absorption, distribution, metabolism, and excretion; mechanism of action of the drug; disease etiology; and/or molecular subtype of the disease being treated. Therefore, where local regulations and IRB/IEC allow, a sample will be collected to enable potential DNA analysis from consenting participants.
- DNA samples may be used for research related to lebrikizumab or CRSwNP and related diseases. They may also be used to develop tests/assays including diagnostic tests related to lebrikizumab and CRSwNP. Genetic research may consist of the analysis of one or more candidate genes or the analysis of genetic markers throughout the genome or analysis of the entire genome (as appropriate).
- The samples may be analyzed as part of a multistudy assessment of genetic factors involved in the response to lebrikizumab or study interventions of this class to understand the study disease or related conditions.
- The sponsor will store the DNA samples in a secure storage space with adequate measures to protect confidentiality.
- The samples will be retained while research on lebrikizumab continues but no longer than 15 years or other period as per local requirements.

## **9 Statistical Considerations**

This section summarizes the planned statistical analysis strategy and procedures of the CRSwNP study. The details of statistical analysis will be provided in a statistical analysis plan (SAP), which will be finalized prior to unblinding of IP assignments. Changes from analyses planned in this protocol will be documented in the SAP. Any deviations from the

planned analysis as described in the SAP will be justified and recorded in the clinical study report.

Because all adolescent patients receive lebrikizumab Q2W/Q4W treatment on an open-label basis, no statistical hypothesis will be tested, and no inferential statistical analysis will be performed. Adolescent participants' data will be summarized separately using descriptive statistics and listings based on all observed data. The number and percentage of adolescent participants experiencing ICEs will also be summarized.

All statistical sections below refer to the analysis of adult participants unless otherwise specified.

## 9.1 Estimands and Intercurrent Events

### 9.1.1 Intercurrent Events

According to ICH E9(R1) addendum, estimands should be constructed to directly address the ICEs that could affect the interpretation of treatment effect. Therefore, the following ICEs are considered for the primary endpoint analysis of this study (Table 9-1).

**Table 9-1 Intercurrent Event Types**

Label	ICE Types
ICE1 (Discontinuation of IP)	Discontinuation of IP due to any reasons
ICE2 (Steroid Use – Short-Term)	Short-term use of SCS treatment (1 mg/kg prednisone equivalent per day for ≤7 days of use)
ICE3 (Steroid Use – Long-Term)	Long-term use of SCS treatment (greater use than the definition for short-term use above) or long-term use of nasal saline lavage with corticosteroids (>10 days)
ICE4 (Surgery)	Undergoing nasal polyp surgery
ICE5 (Change to Other Biologics)	Change to another approved biologic therapy for CRSwNP

Abbreviations: CRSwNP = chronic rhinosinusitis with nasal polyps; ICE = intercurrent event; IP = investigational product; SCS = systemic corticosteroids.

Any SCS treatments separated by less than 7 days will be considered continuous treatment. Nasal saline lavage with corticosteroid treatments separated by less than 3 days will be considered continuous treatment.

### 9.1.2 Estimands

Table 9-2 presents the primary estimand and rationale for strategies to address ICEs.

**Table 9-2 Primary Estimand with Rationale for Strategies to Address Intercurrent Events**

Primary Estimand	
Estimand Description (summary below)	Differences in means will be compared between participants treated with lebrikizumab and PBO in combination with background INCS, regardless of treatment discontinuation or short-term use of SCS treatment ( $\leq 1$ mg/kg prednisone equivalent per day for $\leq 7$ days of use). Nasal polyp surgery, change to another approved biologic therapy, or long-term use of SCS or nasal saline lavage with corticosteroids will be considered as treatment failures. In the case of treatment failure, values will be replaced with the worst possible scores.
Endpoint	Primary and key secondary endpoints
Treatment Conditions of Interest	Lebrikizumab versus PBO in addition INCS.
Target Population	Participants with CRS with bilateral NP
Population-Level Summary	Difference in means between lebrikizumab and PBO
ICEs and Strategies to Handle ICEs	
ICE1 (Steroid Use – Discontinuation of IP)	Treatment policy
ICE2 (Steroid Use – Short-Term)	Treatment policy
ICE3 (Steroid Use - Long-Term)	Composite
ICE4 (Surgery)	Composite
ICE5 (Change in Other Biologics)	Composite
Rationale for Strategies	To estimate the treatment effect irrespective of discontinuation of IP and short-term SCS use.  The composite strategy is used to set the worst possible score for long-term steroid use, surgery, and change to another approved biologic as this is considered to be treatment failure.

Abbreviations: CRS = chronic rhinosinusitis; ICE = intercurrent event; INCS = intranasal corticosteroid; IP = investigational product; NP = nasal polyp; PBO = placebo; SCS = systemic corticosteroids.

Note: Refer to Table 9-1 for specific numbered ICE definitions.

## 9.2 Statistical Hypothesis

The following hypotheses will be tested to demonstrate the superiority of lebrikizumab 250 mg Q2W over PBO in reducing study participants' reported nasal congestion along with an objective assessment of NP in participants with CRS with bilateral NP on background therapy with INCS at Week 24.

- Null hypothesis (H10): The mean CFBL in endoscopic NPS at Week 24 for the lebrikizumab 250 mg Q2W group is equal to that for the PBO group.
- Alternative hypothesis (H1a): The mean CFBL in endoscopic NPS at Week 24 for the lebrikizumab 250 mg Q2W group is not equal to that for the PBO group.

and

- Null hypothesis (H20): The mean CFBL in NCS severity at Week 24 for the lebrikizumab 250 mg Q2W group is equal to that for the PBO group.
- Alternative hypothesis (H2a): The mean CFBL in NCS severity at Week 24 for the lebrikizumab 250 mg Q2W group is not equal to that for the PBO group.

## 9.3 Sample Size Determination

The planned sample size for adults is approximately 510 participants, with 170 participants in the PBO group and 340 participants across the 2 lebrikizumab dose groups. The adult sample size was determined to enable an adequate characterization of the differences in efficacy between lebrikizumab 250 mg Q2W and PBO with regard to mean changes from baseline in NCS severity and endoscopic NPS at Week 24. This planned sample size was calculated based on the treatment effect observed in SINUS-24 and SINUS-52 ([Bachert et al 2019](#)) and uses the assumption that the mean difference in CFBL in NCS severity between lebrikizumab and PBO is 0.62 with common standard deviation (SD) 1.0, and the mean difference in CFBL in endoscopic NPS is 1.48 with common SD 2.1. Assuming normal distribution and no negative correlation between the 2 endpoints and 20% dropout rate, a sample size of 170 participants per arm is expected to be sufficient to provide a combined power of 99% using a 2-sided t-test with alpha of 0.01 for changes from baseline in NCS severity and endoscopic NPS at Week 24. In addition to the co-primary endpoints, the sample size also allows sufficient power for the key secondary endpoint of time-to-event for participants

receiving systemic corticosteroids, and/or approved biologics for CRSwNP rescue use, and/or planned surgery. Assuming the probability of having such rescue events during study treatment period is 27% in the placebo group, and is 10% in the lebrikizumab group, with 170 patients per arm, the study will have approximately 90% power to detect a hazard ratio of 0.35 between the treatment groups using a 2-sided log-rank test with alpha of 0.01. The sample size was calculated using nQuery Version 9.1.

Approximately 1020 adult participants will be screened to achieve 510 randomly assigned to IP. The study will use block randomization with fixed block size and be stratified based on 3 factors: asthma and/or AERD versus no asthma/no AERD, prior NP surgery versus no prior NP surgery, geographic region (North America, Europe, rest of the world). Adult participants without asthma and/or AERD history will be limited to approximately 255 participants (out of the total 510 randomized participants). Adult participants without prior surgery will be limited to approximately 255 participants (out of the total 510 randomized participants). Adult participants may fall in more than one category without limitation in numbers.

Adolescents are not included in the above planned sample size and will be enrolled on an open-label basis to the lebrikizumab Q2W/Q4W treatment arm. No specific sample size is targeted for the adolescent population. The study design will allow as many adolescents to be enrolled as possible as long as the adult enrollment period is still open.

## 9.4 Analysis Sets

The following participant analysis sets will be used in the statistical analyses for adults and adolescents separately. The analysis sets refer to the adult participants only unless otherwise specified. The corresponding adolescent analysis sets follow the same definition of adult analysis sets except for including adolescent participants only, e.g. Adolescent Intent-to-Treat Analysis Set.

All Entered Analysis Set: The All Entered Analysis Set will consist of all participants who sign the ICF as well as all adolescent patients for whom there is informed consent.

Intent-to-Treat (ITT) Analysis Set: The ITT Analysis Set will consist of all participants who are randomized, even if they do not take the assigned treatment, do not receive the correct treatment, or otherwise do not follow the protocol. Participants will be analyzed according to the treatment to which they are assigned. Unless otherwise specified, efficacy and health

outcomes analyses for the induction period will be conducted on this population.

Safety (SAF) Analysis Set: The SAF Analysis Set will consist of participants who are randomized and received at least one dose of either lebrikizumab or PBO. All analyses using the safety set will group participants according to as randomized.

PK Analysis Set: The PK Analysis Set will consist of all participants in the SAF Analysis Set who have at least 1 PK sample analyzed.

PD Analysis Set: The PD Analysis Set will consist of all participants in the SAF Analysis Set who have at least 1 PD sample analyzed.

Immunogenicity Analysis Set: A participant is evaluable for TE ADA if there is at least 1 non-missing test result for ADA for both the baseline and the postbaseline visits.

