### 8.3.1 Adverse Events

#### 8.3.1.1 Definitions

##### 8.3.1.1.1 AEs

The investigator, or qualified designee, is responsible for reporting all AEs that are observed or reported during the study, regardless of their relationship to the study treatment or their clinical significance.

An AE is defined as any untoward medical occurrence in a participant enrolled into this study, regardless of its causal relationship to the study treatment. Participants will be instructed to contact the investigator at any time after randomization if any symptoms develop.

A treatment-emergent AE (TEAE) is defined as any event not present before exposure to the IP or any event already present that worsens in either intensity after exposure to the IP.

Anticipated day-to-day fluctuations of preexisting diseases or conditions present or detected at the start of the study that do not worsen would not be considered AEs. Laboratory results of disease/disorders being studied and medical/surgical procedures are not AEs but rather the condition/event that leads to it is defined as an AE. Medication error, misuse, or abuse of IP, including any signs, symptoms, or clinical sequelae, are considered AEs.

After the initial report, the investigator is required to proactively follow each participant at subsequent visits or contacts. All SAEs and AEs of special interest (AESIs), as defined in [Section 8.3.1.1.2](#) and [Section 8.3.1.1.5](#), respectively, will be followed until resolution, stabilization, the event is otherwise explained, or the participant is lost to follow-up ([Section 7.3](#)). For product complaints ([Section 8.3.1.1.3](#)), the investigator is responsible for ensuring that follow-up includes any supplemental investigations as indicated to elucidate the nature and/or causality of the AE.

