### **9.5.1 General Considerations**

Data collected in this study will be presented using summary tables, participant data listings and figures. For continuous variables, the number of observations, mean, SD, median, minimum, and maximum will be presented. Categorical variables will be summarized by participant counts and percentages. For ordinal-scaled variables, a combination of presentations may be employed as appropriate: frequency and percentage of observations within a category and means and SDs of the scores of the categories. For categorical and ordinal variables, percentages will be calculated based on the N of the analysis set and number of participants with missing data will also be included. For the efficacy and safety analysis during the induction period, the 2 lebrikizumab arms will be pooled and thus there will be 2 treatment groups. Treatment comparisons for the induction period will be made between lebrikizumab Q2W (pooled) versus PBO.

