### **9.5.9 Safety Analyses**

All the safety analysis will be based on the SAF Analysis Set.

AEs will be coded using MedDRA. The number and percentage of participants reporting TEAEs, treatment-emergent SAEs including deaths, TEAEs considered related to study treatment, and TEAEs leading to discontinuation from IP will be tabulated by treatment group, system organ class (SOC) and preferred term. The TEAEs by maximum severity and relationship will also be tabulated by treatment group, SOC, and preferred term. AEs, SAEs, deaths, and AEs leading to discontinuation will be listed by participant.

Descriptive statistics for laboratory test results (hematology, clinical chemistry, and urinalysis) will be provided for the observed values and changes from baseline at each scheduled visit. A shift table (abnormal low/normal/abnormal high) will be provided for select laboratory tests.

Descriptive statistics by treatment group will be provided for the observed values and CFBL at each scheduled visit with vital signs assessment.

Results of the physical examinations will be summarized by visit using appropriate descriptive statistics.

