## **9.5.11 Other Analyses**

Summary statistical analyses will be provided for demographics, baseline disease characteristics, medical history, and other characteristics.

Participant disposition will be summarized by treatment or by treatment sequence for each period and include the number of participants in the ITT Analysis Set who completed or withdrew from treatment for each period, as well as the number of participants in each analysis set.

The number of participants who withdrew from IP and withdrew from study will be summarized by treatment or by treatment regimen for each period and the reason for withdrawal.

Medical history will be coded according to the latest version of MedDRA and will be summarized by SOC and preferred term.

The number and percentage of participants with prior and concomitant medications will be tabulated by Anatomical Therapeutic Chemical Classification System of WHO Drug Global dictionary, preferred term, and actual treatment received (or treatment sequence). A medication's usage will be considered concomitant if it was started or continued after the first administration of the IP. If the start date is missing, it will be assumed that the medication was used concomitantly. Details on handling partial dates (ie, year or only year and month) will be described in the SAP.

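### Safety tables group adults as randomised but the medication table uses treatment received; any cross-arm dosing error would slightly dilute the safety contrast

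*Protocol*

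**What the plan says.** Section 9.4 of the protocol admits to the Safety Analysis Set "participants who are randomized and received at least one dose of either lebrikizumab or PBO". Membership therefore depends on having been dosed, but the grouping does not: "All analyses using the safety set will group participants according to as randomized".

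Section 9.5.9 makes that rule cover all of safety: "All the safety analysis will be based on the SAF Analysis Set". Adverse events "will be tabulated by treatment group, system organ class (SOC) and preferred term", with no exception for participants who received something other than their assigned product. For the induction period, Section 9.5.1 says that "the 2 lebrikizumab arms will be pooled and thus there will be 2 treatment groups".

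The protocol expects that wrong treatment can occur. The ITT set in Section 9.4 keeps participants "even if they do not take the assigned treatment, do not receive the correct treatment, or otherwise do not follow the protocol". Section 8.3.1.1.1 adds: "Medication error, misuse, or abuse of IP, including any signs, symptoms, or clinical sequelae, are considered AEs".

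Section 9.5.11 tabulates prior and concomitant medications by "preferred term, and actual treatment received (or treatment sequence"). It names no analysis set for this table. The protocol neither defines actual treatment received nor explains why this table has a different basis from the safety tables.

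**The concern.** Grouping as randomised is the right default for efficacy, where it preserves the randomised comparison. For safety the question is what happened to people exposed to the drug. If a placebo-randomised adult is given lebrikizumab and then has an event that the drug makes more likely, counting it under placebo raises the placebo rate. An error in the other direction lowers the drug rate. Either way the difference shrinks, which is not conservative when looking for harm.

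The mismatch with Section 9.5.11 is a separate, smaller problem. The same participant could appear under placebo in the adverse event table and under lebrikizumab in the medication table, and a reader comparing the two would find groups that do not match.

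This is not a detail left to the SAP. The protocol states the rule for all analyses of the set, and under Section 9 the SAP would have to document any departure as a change from the protocol.

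**Working it through.** The protocol gives no figure to reproduce here and no rate of dosing errors. The check is a comparison of the text, followed by an illustration on stated assumptions.

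**Text**

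- Safety summaries (Sections 9.4 and 9.5.9): as randomised, without exception.
- Prior and concomitant medications (Section 9.5.11): actual treatment received or treatment sequence.
- Adolescents (Section 9): all assigned to open-label lebrikizumab and summarised separately, so the question does not arise for them.

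**Where errors could occur**

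Tables 6-2 and 6-3 give 12 + 8 = 20 dosing dates per adult. Two dates carry two injections, so there are 22 injections. Away dosing is the default on 6 + 6 = 12 of the 20 dates. In maintenance the Q2W/Q8W arm receives placebo on 4 of its 8 dates by design, so receiving a placebo injection does not by itself show an error.

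**Illustration 1: a fairly common event**

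Inputs: 170 placebo and 340 lebrikizumab adults (Section 9.3), all assumed dosed. Assumed event rates are 8% on drug and 2% on placebo. *m* placebo participants are misdosed and are assumed to carry the full drug rate.

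Placebo rate as tabulated = [(170 − m) × 0.02 + m × 0.08] / 170

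| m | Calculation | Placebo rate | Shift (points) |
|---|---|---|---|
| 1 | (3.38 + 0.08)/170 | 2.04% | 0.04 |
| 2 | (3.36 + 0.16)/170 | 2.07% | 0.07 |
| 5 | (3.30 + 0.40)/170 | 2.18% | 0.18 |

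With m = 2 the difference falls from 6.00 to 5.93 points. A participant given one wrong kit would hardly carry the full drug rate, so these shifts lean high for the assumed rates.

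**Illustration 2: a single rare event**

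One placebo-randomised participant receives lebrikizumab and has the only case.

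- As randomised: placebo 1/170 = 0.59%, lebrikizumab 0/340.
- By treatment received, if the participant is moved: lebrikizumab 1/341 = 0.29%, placebo 0/169.

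The table changes from 0 vs 1 to 1 vs 0 (drug vs placebo). In the extreme case where 1 to 5 participants are misdosed and all have the event, the placebo rate rises by 1/170 to 5/170, or 0.6 to 2.9 points.

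**The case against.** The strongest reply is that Section 9.4 states one clear rule by choice. It keeps the same participants per arm in efficacy and safety, and nothing in the protocol shows it to be an error. That is fair: this is a choice with a small, avoidable cost, not a mistake of fact.

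The next reply is that the contradiction is narrow, and this stands. A reader might infer that Section 9.5.11 sets a competing rule for adverse events. It does not: its wording covers only the prior and concomitant medication table, and Section 9.5.9 follows Section 9.4.

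A reader might also infer that rare serious events in misdosed participants would be lost or wrongly attributed altogether. The protocol does not support that. Section 9.5.9 lists adverse events, serious events, deaths and events leading to discontinuation by participant. Section 8.3.1.2.2 names an administration error among the possible contributing factors for each serious event. Section 6.5 requires dosing deviations to be recorded, and eosinophil disorders, hypersensitivity and infections have their own eCRF pages (Section 8.3.7). Only the column of the summary table is affected.

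Errors should also be uncommon: assignment is central (Section 6.3), and a second staff member confirms dose and identity at clinic dosing (Section 6.5), although that check does not reach home dosing.

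Finally, simply switching to treatment actually received would replace a clear rule with an undefined one. With 20 dosing dates, an error would plausibly affect one or a few kits. A majority-of-doses rule would leave the event under placebo, exactly as now. This objection stands, and the fix must answer it.

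**Conclusion.** The point holds in a limited form. The safety summaries and the medication table use different bases, and the safety basis would count events after lebrikizumab given in error to a placebo-randomised adult under placebo.

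The effect is zero if no cross-arm error occurs. With 1 to 5 misdosed placebo participants and the assumed rates of 8% and 2%, the placebo rate shifts by about 0.04 to 0.18 points. Only for a single rare event could one case visibly change a summary table, and the participant listings would still allow it to be traced. The number of errors and the event rates are assumptions. Efficacy, power and the ITT analyses are not affected. This is a minor improvement, worth making because it is nearly free.

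**What to change.** In Section 9.4, group Safety-set analyses by treatment actually received and define the term at regimen level. For example:

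- An adult randomised to placebo who receives any lebrikizumab dose is counted under lebrikizumab for safety.
- Planned placebo injections in the Q2W/Q8W arm do not change a participant's group.
- For the induction period there is one pooled lebrikizumab group. For tables that separate the two maintenance regimens, the definition must also say which group takes such a participant.

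Keep ITT as randomised, list every participant whose received and randomised treatments differ, and refer to the same definition in Section 9.5.11.

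If the sponsor prefers to keep safety as randomised, the minimum is that listing, a sensitivity table by treatment received, and alignment of Section 9.5.11.

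The cost is a few sentences, since Section 9.5.11 already requires an actual-treatment variable. There are two downsides. Safety and ITT group sizes may differ by a few participants. Under an any-dose rule, a mostly placebo course, including events before the wrong dose, may be counted under drug; the listing lets a reader see those cases.
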